1. VERSION HISTORY

Table 1. Summary of Changes

Table 1. Summary of Changes

Version/ Date	Associated Protocol Amendment	Rationale	Specific Changes
	Amenument		Added Flag Level categories for eGFR in Table 3 Clincial Laboratory Parameters (Section 3.5.2)
			Removed derived non-HDLC in hematology analytes as direct VLDL is being collected instead and added other Biomarkers (or components) that should be based on samples collected in a fasted state(Section 3.5.2)
			Added categories for heart rate in ECG criteria of clinical concern (Section 3.5.3)
			Updated missing data handling for hypothetical estimands (Sections 4, 5.3, Appendix 1)
			Changed 'CI' to 'credible interval' for results obtained from Bayesian Emax model (Sections 5.2.1, 5.2.2, 6.1.1, 6.2.1, 6.2.2, 6.2.3, 6.2.4, 6.3.3, 6.3.5)
			Changed '95%' to 90% CIs/credible intervals except for the 3-tier approach for the analysis of adverse events (Sections 5.2.1, 5.2.2, 6.1.1, 6.2.1 to 6.2.5, 6.3.1 to 6.3.6)
			Added clarification that Total Daily Dose will be used in Bayesian Emax modeling (Section 5.2.1)
			Added estimation of risk difference in treatment comparisons (Sections 5.2.1, 6.1.1, 6.2.1 to 6.2.4, 6.3.1 to 6.3.5)
			Added specification on Bayesian Emax modeling for liver fat (Sections 5.2.2, 6.2.5)

Table 1. Summary of Changes

Version/ Date	Associated Protocol Amendment	Rationale	Specific Changes
			Added instructions on how to handle non-evaluable histological change from baseline data (Section 5.3)
			Added specifications for supplementary analyses of the primary endpoint (Section 6.1.1.2)
			Added prior estimates for the Bayesian Emax modeling of liver fat (Section 6.2.5)
			Added specifications for the analyses of other continuous tertiary endpoints (Section 6.3.6)
			Added a criterion for exclusion of samples in PK summaries (Section 6.3.8)
			Removed text describing the summary of participant disposition by pre-defined medical history terms (Section 6.5.2)
			Increased the number of categories for which the number of participants differing numbers with prespecified medical histories will be summarized (Section 6.5.4)
			Added specification for individual plots to be produced for selected laboratory parameters (Section 6.6.2)
			Added references to estimands and additional exploratory endpoints to the Summary of Effiacy Analyses (Appendix 1)

Table 1. Summary of Changes

Version/ Date	Associated Protocol	Rationale	Specific Changes
2	Amendment		
			Added clarifications in analysis visit windows (Appendix 2.1)
			Added clarification for % liver fat derivation (Appendix 2.2.1)
			Added specification for the derivation of NASH Symptom Diary Score (Section 2.3.3)
			Added specification for the derivation of MELD score (Appendix 2.4.2)
			Added specification for the derivation of AUDIT Total Score (Appendix 2.4.4)
Version 2/	Amendment 1	Clarification of	Updated the definition of estimands by
06 Apr 2022	30 August 2021	analyses or	removing the phrase "the study
001412022	201108000 2021	additional	population of randomized and
		details added to	• •
		prior version	inferential population (Sections 2.1.1,
		and updates to	2.1.2, 2.1.3, 3.1)
		reflect Protocol	
		Amendment 1	Throughout the document, ensured that
		Amendment 1	the term participants has been used
			when referring to subjects consented into this study
			Added exploratory estimand to assess endpoints related to worsening in liver biopsy components as well as capture qualitative assessment on each of 4 domains of histological assessments (Sections 2.1.3, 6.3.1, 6.3.2, Appendix 1)
			Applied changes made in Protocol Amendment 1 related to the discontinued evaluation of 2 arms with administration of DGAT2i alone (150

Table 1. Summary of Changes

Version/ Date	Associated Protocol Amendment	Rationale	Specific Changes
	Amenument		mg QD and 300 mg QD) (Sections 2.2, 4, 4.1, 5.1, 5.2, 5.2.1)
			Updated the hypothetical estimand definition to include information on censored data (Sections 2.1.2, 2.1.3, 4, Appendix 1)
			Added additional details about the definition and derivation of the primary endpoint, and biopsy assessments (Section 3.1)
			Added CCI and CCI as exploratory endpoints (Section 3.3, 6.3.3, Appendix 2.2.1, Appendix 2.2.3)
			Added derivation of baseline vital signs (Section 3.4)
			Added clarification on the definition of treatment emergent adverse events (Section 3.5.1)
			Added clarification on laboratory parameters (Section 3.5.2 and Appendix 2.4)
			Updated the formula for QTcF, definition of changes in background medications of special interest, data to be summarized for AUDIT, and analysis of DILI (Section 3.5.3)
			Added exclusion of participants from Evaluable and Safety Analysis Sets for issues related to quality of protocol execution leading to a Sponsor decision to prematurely withdraw randomized participants and close site(s) (Section 4)

Table 1. Summary of Changes

Version/ Date	Associated Protocol Amendment	Rationale	Specific Changes
	Amendment		Updated the definition of Enrolled, Evaluable and Safety Set to explain how participants originally randomized to the 2 DGAT2i QD groups will be handled (Section 4)
			Added defined analysis data set for biopsy-based composite estimands related to worsening in liver biopsy components and updated the definition of defined analysis data set for hypothetical estimands (Section 4)
			Corrected the derivation of percent change from baseline in the analysis of log-transformed continuous endpoints to first determine the relative change from baseline (Section 5.2.2, 6.2.5.1, 6.3.3.1)
			Updated the description of MMRM analysis (Sections 5.2.2, 6.3.3.1)
			Added derivation of date of birth (Section 5.3)
			Added supplementary analyses to assess quality of biopsy assessments (6.1.1.2)
			Updated the list of event-based exploratory endpoints that will be summarized based on the pre-specified events undergoing adjudication (Section 6.3.4.1)
			Removed subset analysis on LFT endpoints in participants with ALT>ULN at baseline (Section 6.4)
			Added demographic and baseline characteristics variables to be summarized (Section 6.5.1)

Table 1. Summary of Changes

Version/ Date	Associated Protocol Amendment	Rationale	Specific Changes
			Updated description of baseline and other summaries (Section 6.5) Changed the percentages of randomized participants to be used to trigger the interim analyses (Section 7.1)
			Clarified data inclusion and handling of intercurrent events and missing data in efficacy analyses (Appendix 1)
			Updated definition and use of visit windows (Appendix 2.1)
			Incorporated additional clarification to endpoint derivations (Appendix 2.2)
Version 1/ 31 Mar 2020	Original 22 Jan 2020	N/A	N/A

2. INTRODUCTION

This Statistical Analysis Plan (SAP) provides the detailed methodology for summary and statistical analyses of the data collected in Study C2541013 (MIRNA). This document may modify the plans outlined in the protocol; however, any major modifications of the primary endpoint definition or its analysis will also be reflected in a protocol amendment.

2.1. Study Objectives, Endpoints, and Estimands

2.1.1. Primary Estimand(s)

• Estimand 1.1: Using a composite estimand strategy in patients with biopsy-confirmed NASH and fibrosis on eligibility assessment of SCR2 biopsy, estimate the treatment effect of Diacylglycerol acyltransferase 2 inhibitor (DGAT2i) doses administered alone and coadministration of DGAT2i + Acetyl-CoA carboxylase inhibitor (ACCi) relative to placebo, and coadministration of DGAT2i + ACCi, relative to DGAT2i alone, in terms of the proportion of 'clinical responders', defined as participants achieving centrally adjudicated: resolution of Nonalcoholic steatohepatitis (NASH) without worsening of fibrosis or improvement in fibrosis by ≥1 stage without worsening of NASH, or both, at Week 48 and treating all cases of withdrawal from treatment for lack of efficacy or toleration as non-responders.

The main intercurrent event of withdrawal from treatment for lack of efficacy or toleration is addressed as part of the responder variable definition, therefore this is not handled separately. Participants who withdraw from treatment for other reasons but have evaluable biopsy data at withdrawal or at Week 48 will have their biopsy data assessed to determine whether they are responders or not. Participants with no Week 48 biopsy data will be considered to be non-responders. All treatment effect contrasts will be obtained through fitting the Bayesian dose-response (DR) and/or exposure-response (ER) models with a logit transformation, or logistic regression models.

2.1.2. Secondary Estimand(s)

Secondary estimands to assess secondary objectives will be:

- Estimand 2.1: Using a composite estimand strategy, in patients with biopsy-confirmed NASH and fibrosis, on eligibility assessment of SCR2 biopsy as assessed by the sponsor-identified central pathologist(s), estimate the treatment effect of DGAT2i doses administered alone and coadministration of DGAT2i + ACCi relative to placebo, and coadministration of DGAT2i + ACCi, relative to DGAT2i alone, in terms of the proportion of 'clinical responders', defined as participants achieving centrally adjudicated resolution of NASH without worsening of fibrosis, at Week 48 and treating all cases of withdrawal from treatment for lack of efficacy or toleration as non-responders. Participants who withdraw from treatment for other reasons but have evaluable biopsy data at withdrawal or at Week 48 will have their biopsy data assessed to determine whether they are responders or not. Participants with no Week 48 biopsy data will be considered to be non-responders. All treatment effect contrasts will be obtained through fitting the Bayesian dose-response and/or exposure-response models with a logit transformation, or logistic regression models.
- Estimand 2.2: Using a composite estimand strategy, in patients with biopsy-confirmed NASH and fibrosis, on eligibility assessment of SCR2 biopsy as assessed by the sponsor-identified central pathologist(s), estimate the treatment effect of DGAT2i doses administered alone and coadministration of DGAT2i + ACCi relative to placebo, and coadministration of DGAT2i + ACCi, relative to DGAT2i alone, in terms of the proportion of 'clinical responders', defined as participants achieving centrally adjudicated improvement in fibrosis by ≥1 stage without worsening of NASH, at Week 48 and treating all cases of withdrawal from treatment for lack of efficacy or toleration as non-responders. Participants who withdraw from treatment for other reasons but have evaluable biopsy data at withdrawal or at Week 48 will have their biopsy data assessed to determine whether they are responders or not. Participants with no Week 48 biopsy data will be considered to be non-responders. All treatment effect contrasts will be obtained through fitting the Bayesian dose-response and/or exposure-response models with a logit transformation, or logistic regression models.
- Estimand 2.3: Using a composite estimand strategy, in patients with biopsy-confirmed NASH and fibrosis, on eligibility assessment of SCR2 biopsy as assessed by the sponsoridentified central pathologist(s), estimate the treatment effect of DGAT2i doses administered alone and coadministration of DGAT2i + ACCi relative to placebo, and DMB02-GSOP-RF02 5.0 Statistical Analysis Plan Template 05-Dec-2019

coadministration of DGAT2i + ACCi, relative to DGAT2i alone, in terms of the proportion of 'clinical responders', defined as participants achieving centrally adjudicated improvement in fibrosis by ≥2 stages without worsening of NASH, at Week 48 and treating all cases of withdrawal from treatment for lack of efficacy or toleration as non-responders. Participants who withdraw from treatment for other reasons but have evaluable biopsy data at withdrawal or at Week 48 will have their biopsy data assessed to determine whether they are responders or not. Participants with no Week 48 biopsy data will be considered to be non-responders. All treatment effect contrasts will be obtained through fitting the Bayesian dose-response and/or exposure-response models with a logit transformation, or logistic regression models.

- Estimand 2.4: Using a composite estimand strategy, in patients with biopsy-confirmed NASH and fibrosis, on eligibility assessment of SCR2 biopsy as assessed by the sponsor-identified central pathologist(s), estimate the treatment effect of DGAT2i doses administered alone and coadministration of DGAT2i + ACCi relative to placebo, and coadministration of DGAT2i + ACCi, relative to DGAT2i alone, in terms of the proportion of 'clinical responders', defined as participants achieving centrally adjudicated improvement of ≥2 points in Total Nonalcoholic fatty liver disease (NAFLD) Activity Score (NAS) without worsening of fibrosis at Week 48 and treating all cases of withdrawal from treatment for lack of efficacy or toleration as non-responders. Participants who withdraw from treatment for other reasons but have evaluable biopsy data at withdrawal or at Week 48 will have their biopsy data assessed to determine whether they are responders or not. Participants with no Week 48 biopsy data will be considered to be non-responders. All treatment effect contrasts will be obtained through fitting the Bayesian dose-response and/or exposure-response models with a logit transformation, or logistic regression models.
- Estimand 2.5: Using a hypothetical estimand strategy, in patients with biopsy-confirmed NASH and fibrosis, on eligibility assessment of SCR2 biopsy as assessed by the sponsor-identified central pathologist(s), estimate the treatment effect of DGAT2i doses administered alone and coadministration of DGAT2i + ACCi relative to placebo, and coadministration of DGAT2i + ACCi, relative to DGAT2i alone, in terms of population level average percentage change from baseline in liver fat (assessed via Magnetic resonance imaging using proton density fat fraction acquisition (MRI-PDFF)) at Week 48, assuming all participants had remained in the trial and received treatment as planned without withdrawal up to 48 weeks. Endpoint data collected after treatment withdrawal will be censored. All treatment effect contrasts will be obtained through fitting the Bayesian dose-response and/or exposure-response models, or Analysis of covariance (ANCOVA) models.

2.1.3. Additional Estimand(s)

A secondary estimand to assess the primary objective will be:

 Estimand 1.2: Using a hypothetical estimand strategy, in patients with biopsy-confirmed NASH and fibrosis, on eligibility assessment of SCR2 biopsy as assessed by the sponsoridentified central pathologist(s), estimate the treatment effect of DGAT2i doses administered alone and coadministration of DGAT2i + ACCi relative to placebo, and coadministration of DGAT2i + ACCi, relative to DGAT2i alone, in terms of estimating the proportion of 'clinical responders', defined as participants achieving centrally adjudicated: resolution of NASH without worsening of fibrosis or improvement in fibrosis by ≥ 1 stage without worsening of NASH, or both, at Week 48, assuming all patients had remained in the trial and received treatment as planned without withdrawal up to 48 weeks. Endpoint data collected after treatment withdrawal will be censored. All treatment effect contrasts will be obtained through fitting the Bayesian dose-response and/or exposure-response models with a logit transformation, or logistic regression models.

This estimand assesses the treatment effect in an alternative, hypothetical setting of adherence to their treatment as planned.

An exploratory estimand to assess endpoints related to worsening in liver biopsy endpoint components at Week 48 is also defined as follows:

 Estimand 3.1: Using a composite estimand strategy, in patients with biopsy-confirmed NASH and fibrosis, on eligibility assessment of SCR2 biopsy as assessed by the sponsoridentified central pathologist(s), estimate the treatment effect of DGAT2i doses administered alone and coadministration of DGAT2i + ACCi relative to placebo, and coadministration of DGAT2i + ACCi, relative to DGAT2i alone, in terms of the proportion of 'clinical responders' (for the purposes of analysis), defined as participants with worsening in liver biopsy endpoint components at Week 48 and treating all cases of withdrawal from treatment for lack of efficacy or toleration also as 'responders'. Participants who withdraw from treatment for other reasons but have evaluable biopsy data at withdrawal or at Week 48 will have their biopsy data assessed to determine whether they are 'responders' or not. Participants with no Week 48 biopsy data will be considered to be 'responders'. Participants who improve or remain the same compared to baseline in their liver biopsy endpoint components are treated as 'non-responders', as response for these endpoints is defined as a worsening in liver biopsy endpoint components. All treatment effect contrasts will be obtained through fitting the Bayesian dose-response and/or exposure-response models with a logit transformation, or logistic regression models.

Finally, exploratory estimands to assess endpoints related to additional definitions of 'clinical response' are defined as follows:

• Estimand 3.2: Using a composite estimand strategy, in patients with biopsy-confirmed NASH and fibrosis, on eligibility assessment of SCR2 biopsy as assessed by the sponsor-identified central pathologist(s), estimate the treatment effect of DGAT2i doses administered alone and coadministration of DGAT2i + ACCi relative to placebo, and coadministration of DGAT2i + ACCi, relative to DGAT2i alone, in terms of the proportion of 'clinical responders', defined as participants achieving improvement in fibrosis by ≥1 stage independent of changes in NAS, at Week 48 and treating all cases of withdrawal from treatment for lack of efficacy or toleration as non-responders.

[figure not shown]
Participants who withdraw from treatment for other reasons but have evaluable biopsy data at withdrawal or at Week 48 will have their biopsy data assessed to determine whether they are responders or not. Participants with no Week 48 biopsy data will be considered to be non-responders. All treatment effect contrasts will be obtained through fitting the Bayesian dose-response and/or exposure-response models with a logit transformation, or logistic regression models.

• Estimand 3.3: Using a composite estimand strategy, in patients with biopsy-confirmed NASH and fibrosis, on eligibility assessment of SCR2 biopsy as assessed by the sponsor-identified central pathologist(s), estimate the treatment effect of DGAT2i doses administered alone and coadministration of DGAT2i + ACCi relative to placebo, and coadministration of DGAT2i + ACCi, relative to DGAT2i alone, in terms of the proportion of 'clinical responders', defined as participants achieving resolution of NASH without worsening of fibrosis and improvement in fibrosis by ≥1 stage without worsening of NASH, at Week 48 and treating all cases of withdrawal from treatment for lack of efficacy or toleration as non-responders. Participants who withdraw from treatment for other reasons but have evaluable biopsy data at withdrawal or at Week 48 will have their biopsy data assessed to determine whether they are responders or not. Participants with no Week 48 biopsy data will be considered to be non-responders. All treatment effect contrasts will be obtained through fitting the Bayesian dose-response and/or exposure-response models with a logit transformation, or logistic regression models.

2.2. Study Design

The detailed set-up of the study is summarized below -

Figure 1. Study Design

This is a multicenter, multinational, randomized, double-blind, double-dummy, placebo-controlled, parallel-group, evaluation of DGAT2i alone, and DGAT2i+ACCi. Approximately 350 participants (50 per arm) with biopsy confirmed NASH with F2-F3 fibrosis, as assessed by sponsor-identified central pathologist(s), will be randomly assigned to the study intervention to ensure approximately 280 evaluable participants (40 per arm) offer evaluable data for the primary objective.

Participants will be randomized in a balanced ratio, using a computer-generated randomization code, to receive either double-blind, double-dummy placebo, 1 of 4 doses/dosing regimens of DGAT2i alone, or 1 of 2 dose-levels of DGAT2i+ACCi for a treatment duration of up to 48-weeks.

For participants randomized before Protocol Amendment 1 is enacted, those randomized to either of the 2 QD (DGAT2i 150 mg QD and DGAT2i 300 mg QD) dosing regimens of DGAT2i alone will remain in the study but will be switched to the corresponding BID dosing regimen of DGAT2i alone, maintaining the assigned total daily dose and the double-blind, double-dummy design. New randomization to the QD treatment arms will cease, after Health Authority (where applicable) and IRB/EC approvals of Protocol Amendment 1. Therefore, following Protocol Amendment 1, participants will be randomized to one of the following treatment arms:

Placebo

DGAT2i (Ervogastat) BID dose arms (for characterization of dose-response):

- DGAT2i 25 mg BID, total daily dose of 50 mg
- DGAT2i 75 mg BID, total daily dose of 150 mg
- DGAT2i 150 mg BID, total daily dose of 300 mg
- DGAT2i 300 mg BID, total daily dose of 600 mg

DGAT2i (Ervogastat) + ACCi (Clesacostat) coadministration dose arms:

- DGAT2i 150 mg BID + ACCi 5 mg BID
- DGAT2i 300 mg BID + ACCi 10 mg BID

The treatment group labels in programmed outputs will be as follows:

Placebo	PF-5571	PF-5571	PF-5571	PF-5571	PF-5571	PF-5571	Tota1
	25 mg	75 mg	150 mg	150 mg	300 mg	300 mg	
	BID	BID	BID	BID+	BID	BID+	
				PF1304 5		PF1304 10	
				mg BID		mg BID	

Following footnote to be included on all tables: PF5571 = Ervogastat and PF1304 = Clesacostat Note: A 'Total' column is required when summarizing baseline of population randomized

The 'PF5571 75 mg BID' group will also include those randomized to DGAT2i 150 mg QD and 'PF5571 150 mg BID' group will also include those randomized to DGAT2i 300 mg QD, therefore, there will be no reference to the QD treatment arms in any of the programmed outputs (including dose at onset for AEs and treatment duration – these will only refer to the BID groups as described above).

3. ENDPOINTS AND BASELINE VARIABLES: DEFINITIONS AND CONVENTIONS

3.1. Primary Endpoint(s)

The Primary Endpoint is the proportion of participants achieving resolution of NASH without worsening of fibrosis or improvement in fibrosis by ≥ 1 stage without worsening of NASH or both, based on assessment by sponsor-identified central pathologist(s), at Week 48, compared to baseline.

In order to derive this endpoint, the components are defined as follows:

- Resolution of NASH: disappearance of ballooning (NAS ballooning score=0) and residual or no lobular inflammation (NAS lobular inflammation score of 0 or 1) and NAS steatosis score of 0, 1, 2 or 3.
- No worsening of fibrosis: no change or a decrease of at least 1 stage in the Brunt-Kleiner scale compared to baseline

and

- Improvement in fibrosis by ≥1 stage: a decrease of at least 1 stage in the Brunt-Kleiner scale compared to baseline
- No worsening of NASH: no change or no increase in NAS for ballooning, inflammation, or steatosis compared to baseline

For all biopsy endpoints evaluating change from baseline, assessment will be based on the paired double pathologist review of digitized slides. As a result of the final paired double pathologist review, if a participant is found not to be eligible for the study (e.g. if they are recategorized as F1 or F4), they will still be included in the analysis. If there has been a different assignment of biopsy grading (e.g. if the final assignment of the baseline biopsy is F3 but at the time of eligibility determination this same biopsy was assessed as F2), then participants will be included in any analyses based on the final paired assessment, rather than the one at the time of eligibility determination, however, the fibrosis grade at eligibility determination (SCR2 Eligibility) will be used as a covariate, as this is what will be used for stratification. Planned biopsy assessments are summarized in Table 2.

- There will be two types of biopsy assessments conducted by the pathologists:
 - Quantitative: NAS grading and fibrosis staging
 - Qualitative: In the blinded side-by-side review, an assessment of which biopsy (SCR2 or Week 48/DC) is considered to be better, worse or are both the same

			(Change from Baseline)	
		review of SCR2 and On-treatment biopsies		
		Limited to only those v	vith on-treatment biopsy	
	SCR2 (for	SCR2 (for Analysis:	On treatment - Wk 48 or	
	Eligibility:	quantitative and	D/C (for Analysis:	
	quantitative	qualitative	quantitative and	
	assessment only)	assessments)	qualitative	
			assessments)	
Pathologist 1	All participants	All participants with	All participants with on-	
parallel review		on-treatment biopsy	treatment biopsy	
Pathologist 2	All participants	All participants with	All participants with on-	
parallel review		on-treatment biopsy	treatment biopsy	
Consensus review	If needed ¹	If needed, for both	If needed, for both	
		quantitative and	quantitative and	
		qualitative	qualitative comparisons ²	
		comparisons ²	_	

Table 2. Biopsy results to be reported for each participant

- Consensus review to reach agreement is not required if both central pathologists agree that (a) either the NAS or Fibrosis grade renders participant ineligible; (b) total NAS score ≥4, with ≥1 for steatosis, inflammation, and ballooning, is met, even if alignment of score for each component of NAS [steatosis, inflammation, ballooning] is absent; and/or (c) fibrosis stage is aligned for higher group [F3 or F4] but may not be aligned for sub-group [F3a, F3b, F4a, F4b]
- Consensus review to reach agreement required for all cases of misalignment on parallel review ie, misalignment on scoring of each component of NAS score, sub-group of fibrosis stage [F3a, F3b, F4a or F4b], qualitative assessment of better, same, worse

Note that Trichrome Stain should only be used for the Fibrosis results and the Hemotoxylin and Eosin Stain should be used for the NAS results, only. Additionally, in change-from-baseline assessment, if there is a Consensus result (i.e. 'PATHOLOGIST 1 AND PATHOLOGIST 2') then this is the one that should be used, and if a Consensus result is not reported, the PATHOLOGIST 1 and PATHOLOGIST 2 results should be identical for all 4 domains (3 related to NAS + 1 related to fibrosis), so either PATHOLOGIST 1 or PATHOLOGIST 2 results can be used.

Mapping of Fibrosis Grades for analysis:

Acceptable Values	Labcorp Result	Fibrosis Grade to use for analysis
0	0 - No fibrosis	0
1a	1a - Zone 3 mild perisin fib	1
1b	1b - Zone 3 mod perisin fib	1
1c	1c - Periportal/portal fib	1
2	2 - Zone 3+ periport/port fib	2

Acceptable Values	Labcorp Result	Fibrosis Grade to use for analysis
3a	3a - Bridging fibrosis (few)	3
3b	3b - Bridging fibrosis (num)	3
4a	4a - Cirrhosis (incomplete)	4
4b	4b - Cirrhosis (established)	4
NON EVALUABLE	Not evaluable	Not evaluable

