5.1. Inclusion Criteria

Participants are eligible to be included in the study only if all of the following criteria apply:

Age and Sex:

- Male or female participants between the ages of 18 (or the minimum country-specific age of consent if >18) and 75 years, inclusive, at PreQ and SCR1;
 - Refer to Appendix 4 for CCI for male (Appendix 4.1) and female (Appendix 4.2) participants.

Type of Participant and Disease Characteristics:

- At PreQ and SCR1, meet ≥ 2 of the following criteria [for laboratory parameters, results must be as assessed by the sponsor-identified central laboratory, with a single repeat permitted to assess eligibility, at each of these 2 visits, if needed]
 - FPG ≥ 100 mg/dL (5.6 mmol/L), or on pharmacological agents with explicit purpose of improving glycemic control (refer to Section 6.5.1);
 - Fasting serum HDL-C <40 mg/dL (1 mmol/L) for males and <50 mg/dL (1.3 mmol/L) for females, or on pharmacological agents with explicit purpose to increase HDL-C (refer to Section 6.5.2);
 - Fasting serum TG ≥150 mg/dL (1.7 mmol/L), or on pharmacological agents with explicit purpose to decrease TG (refer to Section 6.5.2);
 - Seated BP ≥130 / 85 mm Hg, or on pharmacological agents with explicit purpose for BP control (refer to Section 6.5.3);
 - Waist circumference ≥40 inches (102 cm) for males and ≥35 inches (89 cm) for females.

- Meet the following criteria, based on an evaluable FibroScan® as defined in Section 8.1.2.1 (±AST as assessed by sponsor-identified central laboratory); with a single repeat assessment permitted to assess eligibility, if needed, at each of these 2 visits;
 - At PreQ and SCR1, FASTTM score ≥0.30, derived using sponsor-provided NASH tool;

or

- At PreQ and SCR1, meet a combination of
 - CAPTM ≥280 dB/m plus
 - VCTETM between 8.0 and 20.0 kPa, inclusive;
- Eligibility using this non-invasive assessment must occur prior to conduct of screening/baseline liver biopsy at SCR2.
- At SCR2, ultrasound-guided (and in limited cases, other imaging technique(s) as outlined in Section 8.1.1), percutaneous, liver biopsy meeting the NASH CRN definition¹⁴ as determined by sponsor identified central pathologist(s) as follows –
 - A total NAS score of ≥4 (and up to total score of 8) comprising of steatosis grade
 ≥1, plus inflammation grade of ≥1, plus ballooning grade of ≥1;
 - Along with fibrosis of F2 or F3;

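### SAP 3.1 sets no baseline ballooning condition for NASH resolution, so an unchanged biopsy can be coded as a response when the paired baseline re-read already meets the criteria

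*SAP*

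**What the plan says.** SAP Section 3.1 builds the primary endpoint from four components. Resolution of NASH is "disappearance of ballooning (NAS ballooning score=0) and residual or no lobular inflammation (NAS lobular inflammation score of 0 or 1", together with any steatosis score from 0 to 3. The other three components (no worsening of fibrosis, improvement in fibrosis, no worsening of NASH) are each judged against baseline; for example, "No worsening of fibrosis: no change or a decrease of at least 1 stage in the Brunt-Kleiner scale compared to baseline". The resolution bullet has no such phrase, although the endpoint as a whole is stated to be "based on assessment by sponsor-identified central pathologist(s), at Week 48, compared to baseline".

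The baseline is not the read that admitted the participant: "participants will be included in any analyses based on the final paired assessment, rather than the one at the time of eligibility determination". The same paragraph says what happens "if a participant is found not to be eligible for the study" on the re-read: that person is kept and analysed. The examples there concern fibrosis only. Nothing is said about a re-read ballooning score of 0.

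Entry required "inflammation grade of ≥1, plus ballooning grade of ≥1" (Protocol Section 5.1), so a baseline ballooning score of 0 can arise only on the re-read. At the eligibility read, SAP Table 2 waives consensus when both pathologists agree that the NAS criteria are met, "even if alignment of score for each component of NAS [steatosis, inflammation, ballooning] is absent". SAP Section 3.2 carries the same definition into the secondary resolution endpoint.

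**The concern.** The protocol names the endpoint but gives no component scores, so SAP Section 3.1 is what a programmer will code. Coded from its numbers, resolution checks ballooning and inflammation at Week 48 only. A participant re-read at baseline as ballooning 0 and inflammation 0 or 1, with identical scores and the same fibrosis stage at Week 48, would count as resolved although nothing resolved.

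At stake are the reported response rate in every arm and the odds ratios that SAP Section 5.2.1 asks for, in the primary endpoint and in the secondary resolution endpoint. The exploratory endpoint that needs both components (SAP Section 3.3) is not exposed to unchanged slides, because it also requires fibrosis improvement.

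**Working it through.** **1. The scoring rule.** Take all combinations of ballooning (0–2), lobular inflammation (0–3), steatosis (0–3) and fibrosis (0–4): 3 × 4 × 4 × 5 = 240 states. Set Week 48 equal to baseline and apply both limbs of the primary endpoint.
- Absolute scores only: 1 × 2 × 4 × 5 = 40 states are responders. All have baseline ballooning 0 and inflammation 0 or 1.
- With baseline ballooning of at least 1 required: 0 of 240.
- Ballooning 0 alone is not enough. Of the 80 states with ballooning 0, the 40 with inflammation 2 or 3 are not responders.

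**2. The plan's own figure.** Protocol Section 9.2 gives placebo 16%, a theoretical maximum of 60%, ED50 30 mg BID, and a probability of at least 89% of showing a difference above 24% at 150 mg BID. With Emax on the logit scale:
- logit(0.16) = −1.658 and logit(0.60) = 0.405
- at 150 mg: −1.658 + 2.064 × 150/180 = 0.062, so p = 0.515
- difference 0.515 − 0.160 = 0.355
- odds ratio (0.515/0.485) / (0.160/0.840) = 5.57
- SE = √(0.16 × 0.84/n + 0.515 × 0.485/n) = 0.0980 at n = 40 and 0.0877 at n = 50
- P(observed difference > 0.24) = Φ((0.355 − 0.24)/SE) = 0.88 at n = 40 and 0.91 at n = 50

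This brackets the stated 89%. It is a pairwise normal approximation to a Bayesian simulation whose details are not given.

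**3. Effect of the scoring.** Let s be the share re-read at baseline as ballooning 0 and inflammation 0 or 1 (assumed), and k the probability that such a participant is scored a responder. The rate in an arm is (1 − s)p + sk. Take k = 1 for absolute scoring, with all of them staying so and fibrosis not worse. Take k = 0 for scoring them as not resolved, ignoring any response through fibrosis.

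| s | Scoring | Placebo | 150 mg BID | Difference | Odds ratio | P(>0.24), n = 40 | P(>0.24), n = 50 |
|---|---|---|---|---|---|---|---|
| 0 | – | 0.160 | 0.515 | 0.355 | 5.57 | 0.88 | 0.91 |
| 5% | k = 1 | 0.202 | 0.539 | 0.337 | 4.62 | 0.83 | 0.86 |
| 5% | k = 0 | 0.152 | 0.489 | 0.337 | 5.34 | 0.84 | 0.87 |
| 10% | k = 1 | 0.244 | 0.564 | 0.320 | 4.00 | 0.78 | 0.80 |
| 10% | k = 0 | 0.144 | 0.464 | 0.320 | 5.14 | 0.80 | 0.82 |

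The difference is (1 − s) × 0.355 in both rows of each pair, because sk is the same in both arms and cancels. The probability moves by about 1 to 2 points between scorings. What changes is the level of response and the odds ratio. If only half of these participants met the absolute criteria at Week 48 (k = 0.5), placebo would be 0.95 × 0.16 + 0.05 × 0.5 = 0.177 at 5%, or 0.9 × 0.16 + 0.1 × 0.5 = 0.194 at 10%.

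**The case against.** **The wording already implies change.** Ballooning that was absent cannot disappear, and the endpoint is framed against baseline. The limb also checks fibrosis against baseline. This stands as evidence of intent. A reader might infer that the SAP scores resolution on the Week 48 slide alone. The documents do not support that as a flat statement, because the text is ambiguous. But it contains no operative rule for a re-read ballooning score of 0, and the numbers in the bullet point the other way.

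**The case may be rare.** Entry needs ballooning of at least 1, two central pathologists take part, and the paired re-read requires consensus on every misaligned NAS component (SAP Table 2). The documents give no rate, so 5% and 10% are illustrations. Nor do they say whether the 16% placebo estimate already includes such cases.

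**The SAP makes the cases visible.** SAP Section 6.1.1.2 commits to shift tables of the NAS components and to a by-treatment summary of screening biopsies that stay eligible on re-read. These would allow counting, but they do not change responder status. The analysis of discordant baseline reads is optional and unspecified.

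**The risk difference is not rescued.** A reader might infer that false responders shrink the difference and that the fix restores it. The arithmetic does not support this: the loss from 0.355 comes from keeping these participants in the denominator, which the fix also does. Some recovery could come through the fibrosis limb. With assumed fibrosis response of 10% on placebo and 25% on active in this group, a 10% share gives 0.9 × 0.355 + 0.1 × 0.15 = 0.335. Those rates are not in the documents, so no such gain should be claimed.

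**No arm is favoured, and there is no formal test** (SAP Section 5.1). Correct: randomization and blinded reading should spread these cases about evenly.

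**Conclusion.** The concern holds as a gap in the primary responder definition. The stated scores allow an unchanged biopsy to be coded as resolution when the paired baseline re-read has ballooning 0 and inflammation 0 or 1, and the rule that keeps re-read ineligibles leaves such participants in.

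On assumed shares of 5% or 10%, with all of them staying so, placebo response is overstated by about 4 or 8 percentage points (0.202 or 0.244 against 0.160). The crude 150 mg BID versus placebo odds ratio is about 4.6 or 4.0, rather than about 5.3 or 5.1 under scoring as not resolved. The risk difference is not affected by the choice. These figures ignore the fibrosis-stage covariate and use the planning rates. It is worth fixing before unblinding because it concerns the primary endpoint and two analysts could code it differently, not because it threatens the comparison between arms.

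**What to change.** Add to SAP Section 3.1 that the resolution component requires ballooning of at least 1 on the paired baseline read. Where that read is 0, score resolution as not achieved; the participant stays in the analysis and can still respond through the fibrosis component. Apply the same rule to the secondary resolution endpoint in SAP Section 3.2, and pre-specify the absolute-score version as a sensitivity analysis in SAP Section 6.1.1.2.

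The cost is a sentence or two of text and one extra run of an existing analysis. Response rates would be slightly lower in every arm.
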